We will obtain WTS data to investigate transcriptional differences between naïve and long-term users of dupilumab. We will use a GLM to compare gene expression between naïve and long-term users at each visit separately.

The above tests will be performed separately for lesional and non-lesional skin and for children and adults, after which expression differences between naïve and long-term dupilumab users will be compared both between skin types and age cohorts.

Identifying novel AD skin endotypes at all skin sampling time points [EO #4]

Endotype identification analysis will be carried out using WTS data collected from non-lesional/lesional STS and non-lesional/lesional biopsy (adults only) samples at each of the sample time points. Separate analyses will be carried out for children and adults, for STS and biopsy samples, and for non-lesional and lesional skin.

There is no straightforward way to identify endotypes of complex disease. Therefore, we will employ a series of complementary approaches to identify participants with previously defined and novel disease endotypes, which we detail in the SAP. These approaches will either yield gene sets (based on previous studies, DE analysis, or WGCNA) or summary expression states (based on topic modeling; ([Dey et al, 2017](#)) that alone or in combination may capture distinct pathobiological mechanisms of disease.

For each gene set-based endotype identification analysis, we will derive a summary representation of the endotype by treating expression of each gene set as a continuous or a dichotomous variable, in turn. In the case of a continuous variable, we will calculate the geometric mean of expression across each functional gene set. In the case of a dichotomous variable, for each set of endotype genes, we will divide individuals into endotype-high and endotype-low expression categories by hierarchically clustering all participants into $K = 2$ groups based on gene-level expression.

Finally, for expression state-based endotype identification, all participants will be profiled based on their mixture of proportional expression across a range of expression states identified. These membership

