proportions will form the basis of hierarchical clustering of participants into K clusters that correspond to biological subtypes, where the number of groups, K , will be determined based on the data. For each endotype cluster identified using this approach, participants will be dichotomously classified as either endotype-high (a member of the endotype cluster) or endotype-low (not a member of the endotype cluster).

Determining whether novel AD skin endotypes are associated with current mild or moderate-to-severe AD disease [EO #5]

For continuous measures of gene set-based candidate disease endotypes obtained as noted in [Section 13.4.4.4](#), we will determine whether each gene set is associated with AD status or severity by testing whether mean expression across an endotype gene set is associated with disease group identity (mild AD vs. non-AD, moderate-to-severe AD vs. non-AD, and mild AD vs. moderate-to-severe AD) using logistic regression, with expression as the predictor and disease group as the outcome. In the case of a dichotomous variable (high versus low expression of an endotype), we will test whether endotype status is correlated with disease group identity using logistic regression, with endotype status as the predictor and disease group as the outcome.

All analyses will be performed at each time point separately, using current AD status/severity defined at the corresponding visit. Endotypes for lesional/non-lesional skin, children/adults, and STS/biopsies will be analyzed separately.

Determining how AD skin endotypes and gene expression differ among the study outcome groups: (1) topical steroid responders, (2) dupilumab responders, (3) dupilumab non-responders, (4) non-AD, and (5) long-term dupilumab participants [EO #6]

We will determine how AD skin endotypes differ among study outcome groups using the exact same approach as detailed in [Section 13.4.4.5](#), except we will substitute in study outcome group for disease group.

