clinical response described in [Section 13.4.4.7](#). Specifically, we will use a logistic regression model appropriate for repeated measures to predict endotype status (high or low) as a function of visit, clinical response, disease group, and visit x clinical response interaction. The interaction term enables testing for whether the relationship between visit and endotype differs based on clinical response. We will also construct models that predict steroid clinical response as a function of endotype status before treatment. This will enable us to investigate any associations between clinical response to treatment and baseline endotype. Separate analyses will be performed for children and adults, for each endotype (stratified by lesional and non-lesional skin), and for STS and biopsy samples.

Determining whether AD skin endotypes are associated with dupilumab response [EO #12]

Based on AD endotypes identified using both lesional and non-lesional STS and biopsy samples ([Section 13.4.4.4](#)) (dupilumab-naïve topical steroid non-responders only), we will test for an association between skin endotypes and visit, clinical response to dupilumab (using in turn the two body-wide measures described in [Section 13.4.4.7](#)), and an interaction between the two. Specifically, we will use a logistic regression model appropriate for repeated measures to predict endotype status (high or low) as a function of visit, clinical response, disease group, and visit x clinical response interaction. This model will enable us to examine relationships between endotype status and visit as well as determine how these relationships change with clinical response. We will also construct models that predict dupilumab clinical response as a function of endotype status before treatment. Separate analyses will be performed for children and adults, for each endotype (stratified by lesional and non-lesional skin), and for STS and biopsy samples.

Determining whether cell type-specific gene and protein expression and cellular composition differ among AD skin endotypes [EO #13]

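### EO #11 and EO #12 model endotypes only as high/low; the protocol states no within-person visit × response analysis of the continuous endotype score

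*Protocol*

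**What the plan says.** All of this is in Protocol 13.4.4 unless stated.

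- **EO #4** summarises each gene-set endotype by "treating expression of each gene set as a continuous or a dichotomous variable, in turn". For the continuous form, "we will calculate the geometric mean of expression across each functional gene set". The high/low form comes from "hierarchically clustering all participants into $K = 2$ groups based on gene-level expression". Endotypes identified from expression states get a high/low label only. Endotypes are identified at each sampling time point. Separate analyses are listed for age cohort, sample type and skin type; visit is not in that list. No rule for carrying a classification from one visit to the next is given.
- **EO #5** uses both forms, including "testing whether mean expression across an endotype gene set is associated with disease group identity", at each time point separately. **EO #6** applies the same approach with study outcome group in place of disease group.
- **EO #11 and EO #12** name one form only. The longitudinal model is: "we will use a logistic regression model appropriate for repeated measures to predict endotype status (high or low) as a function of visit", with clinical response, disease group and visit × clinical response as the other terms. The prediction models "predict steroid clinical response as a function of endotype status before treatment" (EO #11) and "predict dupilumab clinical response as a function of endotype status before treatment" (EO #12).
- **Response measures.** EO #11 uses four, of which three are continuous (shifts in TAA, targeted EASI and body-wide EASI). EO #12 uses the body-wide EASI shift and the EASI ≤ 7 split.
- Protocol 13.7.1 gives power for the primary and secondary objectives only. SAP 2.3 sends the exploratory objectives to a separate Exploratory SAP, which was not supplied.

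**The concern.** EO #11 and EO #12 ask whether an endotype tracks or predicts treatment response. The primary objective, EO #5 and EO #6 all keep the continuous summary beside the label. These two objectives do not, and the protocol gives no reason.

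Cutting a graded score at a cluster boundary discards information. It discards most for within-person change, because a participant whose score moves without crossing the boundary counts as unchanged. EO #12 is also small: about 85 adults and 43 children are expected to start dupilumab.

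A second issue follows from the label being relative. Two-group clustering always yields a high and a low group. If it is redone at each visit, part or all of a fall shared by treated participants disappears from the label.

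**Working it through.** **Inputs from the documents.** From 13.7.1: alpha 0.05, 50% type 2-high, and steroid failure of 50% (moderate-to-severe) and 5% (mild). Adult dupilumab starters: 0.5 × 160 + 0.05 × 100 = 85. At 40% response that is 34 vs 51 adults; Table 13.7.1.3 gives 17 vs 26 children. EO #11 splits the dupilumab-naïve participants about 175 vs 85 (adults) and 87 vs 43 (children).

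**Assumptions, not in the documents.** Normal score with SD 1, 50% labelled high, two-sided test, no dropout.

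**1. Reproduce the plan's figure.** The cited formula for a binary predictor with share B high is n = [1.96√(PQ/B) + 0.84√(P1Q1 + P2Q2(1−B)/B)]² / [(P1−P2)²(1−B)]. With B = 0.5, P = 160/260, P1 = 0.700 and P2 = 0.531, n = 260 and the odds ratio is 2.05. Table 13.7.1.1 states 2.06.

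**2. Same formula for EO #12.** With n = 85 and P = 0.40, the label needs an odds ratio of 3.56 for 80% power (P1 = 0.547, P2 = 0.253). With n = 43 and P = 17/43 it needs 6.27.

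**3. Score against label, binary response.** For a difference of d SD, power on the score is Φ(d√[n1n2/(n1+n2)] − 1.96). For 34 vs 51 and d = 0.5: 0.5 × √20.4 = 2.258, and Φ(0.298) = 61.7%. With half of all participants above the cut, 61.8% of one group and 42.1% of the other are high. Comparing those proportions has 42.7% power.

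| Comparison | d (SD) | Score | Label | Loss (points) |
|---|---|---|---|---|
| EO #12 adults, 34 vs 51 | 0.4 | 43.9% | 29.6% | 14.3 |
| | 0.5 | 61.7% | 42.7% | 19.0 |
| | 0.6 | 77.3% | 56.8% | 20.5 |
| | 0.8 | 95.1% | 81.3% | 13.8 |
| EO #12 children, 17 vs 26 | 0.6 | 48.6% | 32.1% | 16.5 |
| | 0.8 | 72.7% | 51.1% | 21.6 |
| EO #11 adults, 175 vs 85 | 0.3 | 62.1% | 43.6% | 18.5 |
| | 0.5 | 96.6% | 85.1% | about 11 |
| | 0.8 | 100% | 99.8% | 0.2 |

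At smaller effects both forms have little power and the gap is smaller: 8.6 points at 0.3 SD for EO #12 adults.

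**4. Continuous response (EASI shift).** Score and response are simulated as correlated normals, with the correlation set so that label against binary response has the odds ratio from step 2.

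| n | Label, binary | Score, binary | Label, EASI shift | Score, EASI shift |
|---|---|---|---|---|
| 85 | 79% | 94–95% | 94% | 99.6% |
| 43 | 80% | 94–95% | 95% | 99.6% |

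At these effects the loss is about 15 points on the binary split and about 5 on the EASI shift.

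**5. Visit × response interaction.** The difference in change was set to give the score about 80% power: (1.96 + 0.84)√[2(1−ρ)]√(1/34 + 1/51), which is 0.62 SD at within-person correlation ρ = 0.5. In simulation with no shared fall, power was 79% for the score and 49% for the label (GEE logistic model). Across ρ = 0.3 to 0.7, both age cohorts and a shared fall of 0 or 0.5 SD, the loss was about 23 to 49 points.

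**6. A truly two-class endotype.** With 34 vs 51 and classes 1 or 2 SD apart, the label loses 4.8 or 3.3 points. At 3 or 4 SD apart it gains 1.8 or 3.9.

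**7. A shared fall (85 participants, ρ = 0.5).** The last two columns use high/low labels.

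| Fall | Score | Re-cut at the median each visit | Fixed baseline cut |
|---|---|---|---|
| 0.3 SD | 77% | 0% | 34% |
| 0.5 SD | 99.8% | 0% | 81% |

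The median re-cut is the extreme case. With two-group clustering and a 1 SD fall, the share labelled high among starters goes from 49% to 50% if starters are clustered alone at each visit. It goes from 70% to 53% if the other groups are clustered with them at each visit (group means assumed), and from 66% to 32% if visits are pooled.

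**The case against.** Much of the case on the other side stands.

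- **The score is not lost to the study.** A reader might infer that the continuous endotype is never set against treatment response. That is wrong: EO #6 tests it between dupilumab responders and non-responders at each time point. EO #8, #9 and #14 also model continuous expression over visits, gene by gene. Neither supplies a within-person visit × response test of the endotype score, and EO #6 covers only the binary split.
- **No single loss figure holds.** A flat 15 points might be read off step 4, but it applies only to the binary split at one chosen effect. EO #12 also plans the EASI shift, where the label already reaches 94–95% at that effect.
- **EO #11 is not a small-group problem.** The 34 vs 51 and 17 vs 26 groups belong to EO #12 alone.
- **The absorbed fall is conditional.** A reader might infer that the label will hide an on-treatment fall. EO #4 does not say that clusters are re-formed at each visit, and it clusters all participants, not starters alone. A fall shared by responders and non-responders would also say nothing about association with response.
- **High/low is defensible for real classes.** Section 1.1 presents AD as distinct subgroups, and step 6 shows that the label then loses little or gains.
- **The Exploratory SAP may already add the score.** That cannot be checked here.

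**Conclusion.** The concern holds in a limited form. As the protocol is written, EO #11 and EO #12 use only high/low status, as outcome and as predictor, although the continuous score is already derived. The gap is the within-person visit × clinical response analysis of that score, and its use to predict the continuous response measures.

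The size depends on assumptions that the documents do not supply (normal score, 50% high, no dropout). For EO #12 the loss is about 14–22 points on binary response at moderate effects. It is about 5 points on the EASI shift, at effects where the label has 80% power on binary response. It is larger for the interaction, and near zero or slightly reversed for a clearly two-class endotype. For EO #11 it runs from about 19 points to near zero. Absorption of a shared fall arises only if status is re-derived by visit.

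The objectives are exploratory, so this is a worthwhile, inexpensive improvement and does not threaten the study's main conclusions.

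**What to change.** In EO #11 and EO #12, in the protocol and the Exploratory SAP, keep the high/low models and add the following for every gene-set endotype:

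1. A linear mixed model of the geometric-mean score with the same fixed effects (visit, clinical response, disease group, visit × clinical response) and a participant random intercept.
2. The pre-treatment score as a predictor in the response models, for the continuous as well as the binary measures.
3. One high/low classification rule for all visits, for example the Day 7 cut carried forward, so that status can change.

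Expression-state endotypes have no planned continuous summary and can stay as they are.

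The cost is some wording and a few extra models, since the score is already calculated. The small downside is that results are per unit of score rather than per endotype-high participant. If the Exploratory SAP already contains these models, only the protocol text needs aligning.

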9.2 Single Cell Proteogenomics

Single-cell proteogenomics (scProteogenomics), in which RNA and protein are sequenced for the same set of cells, will be performed at NJH. Cryopreserved cells from dissociated skin biopsies (see [Section 9.1](#)) will be used to perform sample cell capture. We will stain pooled samples with the Biolegend TotalSeq-A Universal Cocktail and perform single cell capture using the 10X Genomics 3' scRNA-seq workflow, after which the cDNA library and antibody-derived tag libraries will be sequenced on an Illumina NovaSeq 6000. We will use 10X Genomics Cell Ranger software (v3.0.2) to perform all initial data processing to create gene and protein count matrices. Quality control filtering will then be performed to remove suspected doublets, low count cells, and genes/proteins expressed in less than 0.1% of cells. Quality controlled data will be further processed and analyzed as described in [Section 13.4.4.10](#) and in the SAP.

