Using adult skin biopsy samples, we will select archived lesional and non-lesional sample pairs from participants that best represent each of the discovered non-lesional biopsy-based AD endotypes, as well as non-AD samples that contain none of the AD endotypes, for scProteogenomics. Note that if some endotypes exist only in combination with others, we will select the most endotypically pure participants for analysis. We will also consider performing scProteogenomics on participants carrying combinations of AD endotypes that are most strongly associated with AD and/or AD severity.

These selected samples will be processed, integrated, and clustered into cell populations using the same approach described in [Section 13.4.4.10](#), where samples from both visits and skin types will be combined for cell type inference. To then assess changes in cellular composition that underlie AD skin endotypes, we will first explore whether cell types are selectively present or absent in certain AD endotypes. For example, ILC2s or tissue resident T cells may selectively be present in participants who are type 2-high. We will calculate cell type composition in each participant sample and then compare individual cell type proportions between each AD endotype and non-AD controls using beta regression, where different visits and skin types will be analyzed separately. Cell type composition will also be compared between different AD endotypes and non-AD controls using multivariate linear mixed models for compositional data. We will use a similar approach to assess cellular compositional differences between lesional and non-lesional skin and between Day 7 and End of Study Assessments.

To assess differences in gene/protein expression underlying AD endotype, we will identify differentially-expressed genes/proteins between endotype groups (for each cell type, visit, and skin type separately)

using a mixed model. We will assess cell type-specific differences in expression between time points and skin types using a similar approach.

Determining longitudinal changes in skin (skin tape) gene expression across standard-of-care treatment (all timepoints) in the study outcome groups: (1) topical steroid responders, (2) dupilumab responders, (3) dupilumab non-responders, (4) non-AD, and (5) long-term dupilumab participants [EO #14]

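### EO13 names beta regression for cell-type proportions but gives no rule for the exact zeros it expects; a model on cell counts would close the gap

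*Protocol*

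**What the plan says.** Protocol 13.4.4, under EO #13, sets out three looks at cellular composition.

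- An exploratory step: "we will first explore whether cell types are selectively present or absent in certain AD endotypes". The example is that "ILC2s or tissue resident T cells may selectively be present in participants who are type 2-high". No test is named.
- A comparison of single cell types. The plan is to "compare individual cell type proportions between each AD endotype and non-AD controls using beta regression", with one analysis per visit and skin type.
- A joint analysis: "Cell type composition will also be compared between different AD endotypes and non-AD controls using multivariate linear mixed models for compositional data".

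A similar approach is then applied to lesional against non-lesional skin and to Day 7 against End of Study.

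The outcome is one proportion per cell type per sample: "We will calculate cell type composition in each participant sample". The cell types themselves are defined on pooled data, since "samples from both visits and skin types will be combined for cell type inference". The single-cell filter in Protocol 9.2 will "remove suspected doublets, low count cells, and genes/proteins expressed in less than 0.1% of cells". It sets no minimum count or prevalence for a cell type.

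SAP 2.3, 4.3 and 9.3 refer all exploratory analyses to a separate Exploratory SAP, which was not among the supplied documents. The supplied documents contain no rule for zero proportions.

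**The concern.** Beta regression models proportions strictly between 0 and 1. A cell type found in the pooled clustering but missing from one participant's sample has an observed proportion of exactly 0. EO13 expects such samples and treats them as informative. The only test named for single cell types therefore cannot be run as written on the data the objective anticipates.

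The analyst must then delete the zero samples, add a constant, or change the model. If that choice is made after the data are seen, it can decide whether a difference is found and how large it appears. Beta regression in its usual form also ignores how many cells each sample yielded: 3 of 500 cells and 18 of 3,000 cells both enter as 0.6%.

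**Working it through.** The documents give no sample size, cells per sample, cell-type share, overdispersion or power for EO13, so there is no stated figure to reproduce. Every setting in steps 2 to 5 is an assumption.

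**1. The likelihood at zero.** The beta density is proportional to y^(a−1)(1−y)^(b−1), so its logarithm contains (a−1)·log y. With b = 50 and y = 0, it is −∞ for a = 2, +∞ for a = 0.5, and finite (log 50 = 3.91) only in the special case a = 1. A standard beta regression routine stopped with an error when given data containing exact zeros.

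**2. How often zeros occur.** With true share p and n cells, P(no such cell) = (1−p)^n.

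| True share | 500 cells | 1,000 cells |
|---|---|---|
| 0.1% | 0.999^500 = 0.61 | 0.999^1000 = 0.37 |
| 0.5% | 0.08 | 0.007 |
| 1% | 0.007 | 0.000 |

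Variation between samples raises these figures. If the share follows a beta distribution with mean p and precision 50 to 200, the chance of a zero at 500 cells is 0.55 to 0.29 for p = 0.5% and 0.30 to 0.08 for p = 1%.

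**3. What each treatment of zeros does.** Settings: 12 vs 12 samples, 500 to 3,000 cells each, overdispersion parameter 500, shares 0.05% vs 0.3%. The true odds ratio is (0.003/0.997)/(0.0005/0.9995) = 6.0. About 73% and 17% of samples are zeros. Ranges are over repeated simulations of 120 to 250 runs each.

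| Analysis | Median odds ratio | Rejection at 5% |
|---|---|---|
| Beta regression, zeros deleted | 1.7–1.8 | 18–23% (10–12% of datasets not fittable) |
| Beta regression, (y(N−1)+0.5)/N, N = samples | 1.1 | 81–87% |
| Beta regression, (count+0.5)/(cells+1) | 2.5–2.8 | 83–88% |
| Beta-binomial on counts | 5.6–7.1 | 92–93% |

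At 0.1% vs 0.4% (true odds ratio 4.0), the median odds ratios in the same order are 1.75–1.9, 1.12, 2.63 and 4.1–4.2. With no difference, the likelihood-ratio tests rejected in 6 to 9% of runs, so asymptotic p-values are somewhat liberal at this size.

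**4. Why the constant sets the odds ratio.** With N = 24, the first shift adds 0.5/24 = 2.08% to every proportion, which swamps shares of 0.05% and 0.3%. The shifted shares are 0.0005×23/24 + 0.0208 = 0.0213 and 0.003×23/24 + 0.0208 = 0.0237. Their odds ratio is (0.0237/0.9763)/(0.0213/0.9787) = 1.1, so the attenuation is built in. Under the second shift, a zero becomes 0.5/501 = 0.10% at 500 cells but 0.5/3,001 = 0.017% at 3,000 cells.

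**5. A true present/absent mixture.** Settings: 10 vs 10 samples, 500 cells, cell type present in 20% vs 80% of samples, mean share 1% with precision 200 when present. The ratio of mean shares is 0.8%/0.2% = 4.

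- Zeros deleted: median odds ratio 0.95, rejection 7.5%. In 180 of 400 runs a group kept fewer than two samples; these counted as non-rejections.
- Zeros replaced: median odds ratio 1.22 (the N-based shift), 2.16 (0.001) or 2.78 (0.000001). Rejection was 59.5% for the N-based shift and 58.8% for 0.000001.
- Beta-binomial on counts: rejection 82%, and 4.5% with no difference (50% vs 50%). Its median odds ratio was 7.31 against a ratio of 4. At 10% vs 90% it was 21.46 against a ratio of 9.

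**The case against.** A reader might infer that EO13 will miss the presence/absence signal it was written to find. The documents do not support that.

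- Beta regression is one of three approaches, and presence or absence is examined first and separately. This stands for EO13 as a whole. But that step names no test, and the joint compositional model does not clearly fill the gap: if it uses log-ratios, which is not stated, it needs a zero rule too.
- Nothing says that zero samples will be deleted. With a constant added, the power loss in step 3 is roughly 5 to 12 percentage points. This stands: a missed signal follows only from deletion. The effect size still depends on the constant.
- The settings are assumed, and the protocol does not call its example cells rare. At a 1% share and 500 cells, simple sampling gives under 1% zeros. Step 3 also draws data from the beta-binomial family, which favours that model. This stands as a limit on the figures. It does not touch step 1 or the plan's own expectation of absent cell types.
- The Exploratory SAP may already give a zero rule. This cannot be excluded. The protocol names the model, so the two documents would still need to agree.
- Zero-inflated beta regression would also admit zeros. True; but a count model needs no added part for the zeros and uses the number of cells captured.

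A reader might also see the same error in EO10. It has a similar presence/absence step but names no model for comparing single cell-type proportions, so no error is shown there.

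**Conclusion.** The point holds in a limited form. EO13 names a model with no usable likelihood at zero, expects zeros, and gives no rule for them in the supplied documents. Deleting zero samples would remove most of the signal. Adding a constant keeps most of the power but gives an attenuated odds ratio set by the constant: about 1.1 to 2.8 against a true value near 6 under the step 3 settings.

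That zeros break the likelihood needs no assumption. The sizes rest on assumed sample numbers, cell yields, shares and overdispersion, and on simulation error of up to about 4 percentage points (√(0.81×0.19/120) = 0.036). Severity is low: the objective is exploratory, and no sample size or primary or secondary result depends on it.

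**What to change.** - **Endotype vs non-AD comparisons in EO13:** replace beta regression with beta-binomial (overdispersed binomial) regression of the number of cells of each type out of all QC-passed cells in that sample. Keep visits and skin types separate, as planned. Take p-values by permuting the endotype label, keeping each sample's count and total together.
- **Reporting:** beside the odds ratio, give the observed presence frequency in each group, because the ratio can overstate the effect in a true present/absent mixture (step 5). Show the cells captured as well, since presence depends on them (61% vs 37% zeros at 500 vs 1,000 cells in step 2). If one group has no such cell at all, the odds ratio has no finite estimate; the permutation p-value and presence frequencies then carry the result.
- **Paired contrasts in EO13 (lesional vs non-lesional, Day 7 vs End of Study):** use the same count model with a participant random effect, and permute within participant.
- **Compositional model:** if it takes log-ratios, state its zero rule.

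The cost is a wording change in Protocol 13.4.4, matched in the Exploratory SAP, and slightly more computing. The cell counts are already needed to form the proportions, so no new data are required.

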	(dupilumab-naïve participants only) 18. Non-lesional and lesional skin biopsy endotypes determined in exploratory objective 4 (dupilumab-naïve adults only)	determined by skin endotype status.
12. To determine whether AD skin endotypes are associated with dupilumab response	19. Non-lesional and lesional skin tape endotypes determined in exploratory objective 4 (dupilumab-naïve participants only) 20. Non-lesional and lesional skin biopsy endotypes determined in exploratory objective 4 (dupilumab-naïve adults only)	12. The clinical response to dupilumab treatment will be determined by skin endotype status.
13. To determine whether cell type-specific gene and protein expression and cellular composition differ among AD skin endotypes	21. Single cell non-lesional and lesional skin biopsy transcriptome and proteome (adults only)	13. Shifts in the cellular composition of skin and cell type-specific gene and protein expression changes underlie skin endotypes.
14. To determine longitudinal changes in skin (skin tape) gene expression across standard-of-care treatment (all timepoints) in the study outcome groups: (1) topical steroid responders, (2) dupilumab responders, (3) dupilumab non-responders, (4) non-AD, and (5) long-term dupilumab participants	22. Non-lesional and lesional skin tape transcriptome	14. The clinical response to protocol's standard-of-care treatment among different AD participants will be associated with distinct transcriptional trajectories generated across these standard-of-care treatments.
15. To determine whether genetic variation that regulates skin gene expression is associated with AD disease	23. Non-lesional and lesional skin tape and skin biopsy transcriptome 24. Genome-wide genotypes from blood samples	15. Genetic variation drives particular AD skin endotypes.
16. To determine the proteomic profiles of AD lesional and non-lesional skin endotypes	25. Non-lesional and lesional skin tape proteome	16. AD skin endotypes exhibit distinct epidermal protein profiles.
17. To determine the lipidomic and metabolomic properties of AD lesional and non-lesional skin endotypes	26. Non-lesional and lesional skin tape lipidome and metabolome	17. AD skin endotypes exhibit distinct lipid and metabolome profiles.

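### EO13's stated test for individual cell types compares each AD endotype only with endotype-free non-AD controls, so it cannot by itself show a difference among AD endotypes

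*Protocol*

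**What the plan says.** Protocol Table 2.1.3 gives exploratory objective 13 as "To determine whether cell type-specific gene and protein expression and cellular composition differ among AD skin endotypes", with the hypothesis "Shifts in the cellular composition of skin and cell type-specific gene and protein expression changes underlie skin endotypes".

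The analysis is in Protocol Section 13.4.4 under EO #13. Archived adult biopsies are chosen to represent each endotype, "as well as non-AD samples that contain none of the AD endotypes, for scProteogenomics". Four analytic steps follow:

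- An exploratory look: "we will first explore whether cell types are selectively present or absent in certain AD endotypes". The example is a cell type found selectively in type 2-high participants. No test is named.
- The individual cell-type test: "compare individual cell type proportions between each AD endotype and non-AD controls using beta regression", run separately by visit and by skin type.
- An overall composition model: "Cell type composition will also be compared between different AD endotypes and non-AD controls using multivariate linear mixed models for compositional data". Its contrasts are not listed.
- Gene and protein expression tests by mixed model within each cell type, which compare endotype groups with one another.

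SAP Sections 2.3, 4.3 and 9.3 refer all exploratory work to a separate Exploratory SAP, which is not among the documents.

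**The concern.** The objective is a comparison within AD. The only contrast stated for a single cell type is between AD participants with an endotype and people without AD who have no endotype. Everyone on one side has both AD and the endotype; everyone on the other has neither. The test therefore answers whether AD with endotype E differs from endotype-free non-AD skin, and cannot attribute the difference to the endotype rather than to AD.

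What is at stake is the label put on a cell type. If one that is raised in all AD skin is described as underlying a particular endotype, the finding misleads. The label is also reused: EO #15 in the same section asks whether eQTLs lie in genes enriched in the cell types that define particular endotypes.

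**Working it through.** The plan gives no sample size, power or alpha for EO13, so there is no figure to reproduce. The check is first algebraic, then an illustration.

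**What each contrast estimates.** On the logit scale of the beta regression, write the level of a cell type as

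- non-AD: α
- AD with endotype k: α + δ + γ_k

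where δ is the part common to all AD and γ_k the part specific to endotype k. Then

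- endotype k minus non-AD = δ + γ_k (the stated test)
- endotype k minus the average of the other endotypes = γ_k − mean(γ of the others)

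The objective concerns γ. If every γ is zero and δ is not, the stated test is still expected to reject for every k. The second contrast is then zero because δ cancels.

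**Illustration.** Assumed values, none from the documents: three endotypes; mean proportion 0.05 in non-AD and 0.10 in every endotype (no difference among endotypes); beta precision φ = 40; n per group of 8, 15 or 25; two-sided Wald test at 0.05; 400 runs per row. The within-AD contrast sets n participants with one endotype against 2n with the other two.

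| n per group | Each endotype vs non-AD | All three significant | Each endotype vs other AD |
|---|---|---|---|
| 8 | 80.5-81.5% | 63.3% | 4.8-7.8% |
| 15 | 96.3-96.8% | 91.5% | 6.3-9.0% |
| 25 | 99.5-99.8% | 99.0% | 5.0-6.0% |
| 15, no AD shift | 7.0-9.8% | 0.3% | 4.8-7.5% |

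Monte Carlo error near 5% is about √(0.05 × 0.95 / 400) = 1.1 percentage points. The last row shows some small-sample inflation of the Wald test, far too little to explain rates above 80%.

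**Cross-check at n = 15.** With variance μ(1 − μ)/(1 + φ), the average variance is (0.05 × 0.95 + 0.10 × 0.90)/2/41 = 0.06875/41 = 0.001677, so SD = 0.0409. The standardized shift is 0.05/0.0409 = 1.22. Normal-approximation power is Φ(1.22 × √(15/2) − 1.96) = Φ(1.38) = 0.92, the same order as the simulated 96-97%.

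**Can the parallel tests be read side by side instead?** Not reliably. At n = 8 all three endotypes reach significance in 63% of runs, so in about 37% (100 − 63.25) at least one does not, although all three share the same shift. A cell type significant for some endotypes and not others would look selective without any test of that difference.

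**Lesional skin.** EO13 takes lesional and non-lesional pairs and analyses skin types separately. The non-AD schedule in Appendix A lists only a non-lesional biopsy. The stated lesional contrast therefore has no control of the same skin type, and the plan does not say what replaces it.

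**The case against.** Four points can be made for the plan.

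1. *EO13 contains more than this test.* It has the selectivity step, a multivariate model that names different AD endotypes, and expression tests between endotype groups. Nothing in the protocol says that a difference from non-AD will be attributed to an endotype. This stands against a reading that a reader might infer: that EO13 as a whole cannot separate endotypes, or that any AD-wide change will be credited to each of them. The documents do not support that. But the selectivity step names no test, the multivariate contrasts are undefined, and the expression tests concern genes and proteins rather than proportions. None supplies an endotype-versus-endotype test for a single cell type.

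2. *The Exploratory SAP may add the contrast.* It may. The protocol nevertheless states a specific comparator, and that comparator does not match the objective.

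3. *The high rejection rates are power, not error.* Correct. With a true AD shift, rejecting equality with non-AD is the right answer to the question tested. The near-5% rate within AD follows from assuming no endotype effect. The figures show which question each contrast answers; they do not measure an error rate for this trial.

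4. *A within-AD contrast has its own ambiguity.* Also correct. With three endotypes, if γ_F = −1 and the other two are 0, endotype E minus the others is 0 − (−1 + 0)/2 = +0.5, so a fall specific to F looks like a rise in E. The non-AD contrast is needed to show direction, so it should be kept.

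A reader might also infer that endotype-free controls are the extreme end of non-AD and should be drawn at random. The documents do not give the share of non-AD participants who carry an endotype, so this is unsupported. Random selection could also put endotype carriers into the reference group.

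**Conclusion.** The point holds for the individual cell-type test. Its only stated comparator is endotype-free non-AD, which makes endotype and AD status inseparable. It cannot by itself show that a cell type differs among AD endotypes. This follows from the stated contrast and needs no numerical assumption.

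How often a shared shift would be flagged depends on group sizes and shifts that the documents do not give. The simulated rates hold only for the assumed values. Whether shared changes would in fact be misattributed depends on interpretation and on the Exploratory SAP, and the documents settle neither.

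Severity is minor. EO13 is one of 23 exploratory objectives, is run on selected adult biopsies, and carries no stated power or alpha. The primary and secondary objectives do not use it.

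**What to change.** In Protocol Section 13.4.4 (EO #13), or in the Exploratory SAP:

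- For each cell type, within the same visit and skin type, add a beta-regression contrast of AD participants with endotype E against the AD participants selected for the other endotypes. Leave out of the comparator anyone who also carries E.
- Require support from that contrast before calling a cell type endotype-specific, including when the result is carried into EO #15.
- Keep endotype versus non-AD as a separately labelled contrast that gives AD status and direction.
- List the endotype-versus-endotype contrasts of the multivariate composition model.
- State the comparator for lesional skin, since non-AD participants give non-lesional biopsies only.

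The cost is small. The AD samples for the other endotypes are already to be selected, so no further biopsies or assays are needed. There is one more contrast per cell type and endotype at each visit and skin type. Differences within AD are likely to be smaller than differences from non-AD, so fewer will reach significance.
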